**Phase 2:**

- Cycle 1 Day 1: pre-dose and approximately 0.5, 1, 2, 3, 4, 6, 8, and 24 hours after administration of NS-018;
- Cycle 1 Day 15: pre-dose and approximately 2 hours after administration of NS-018; and
- Cycle 2 Day 1: pre-dose and approximately 0.5, 1, 2, 3, 4, 6 and 8 hours after administration of NS-018.

Pharmacokinetic parameters to be estimated include observed maximum concentration (Cmax), time to maximum plasma concentration (Tmax), area under the plasma concentration-time curve (AUC), terminal elimination half-life (t1/2), and accumulation ratio (R).

A twice daily dosing schedule may be initiated based on results from PK analysis.

Additional analysis of excess plasma PK samples may be performed for the further understanding of drug metabolites and for the understanding of drug levels of concomitant medications which might have effected levels (or interfered with measurement) of the experimental product.

## **11 OTHER ASSESSMENTS**

During the Phase I portion of the study, the Myelofibrosis Symptom Assessment Form (MF SAF, see Appendix J) will be completed at baseline and repeated at Cycle 2 Day 1 and Cycle 4 Day 1 and every 3 months thereafter, including End of Study.

During the Phase II portion of the study, the Myeloproliferative Neoplasm Symptom Assessment Form [MPN SAF(MPN-10), see Appendix L] will be completed at baseline and repeated at Cycle 2 Day 1 and Cycle 4 Day 1 and every 3 months thereafter, including End of Study.

Analysis of urine samples from patients in the Phase 2 portion of the study (C1D1, Pre-Dose and Single point, 100ml, 2-6 hours post dose on Cycle 2 Day 1, first 6 patients) will be performed for the further understanding of drug metabolites and for the understanding of drug levels of concomitant medications which might have effected levels (or interfered with measurement) of the experimental product.

## **12 STATISTICS**

Additional statistical analyses, other than those described in this section, may be performed if deemed appropriate. A description of the statistical analysis performed on the study data will be outlined in the Statistical Analysis Plan.

Each phase of this study will be analyzed separately. All tables, figures and listings will therefore be separated by study phase.

Interim analyses of PK, PD, and safety data from the Phase 1 portion of the study will be conducted after the MTD has been established.

An analysis of all existing PK, PD, and safety data from the Phase 2 portion of the study will be conducted 6 months after the last patient is enrolled in this part of the study.

The complete analysis of all study data will be contained in the clinical study report at the end of the study.

## 12.1

### Sample Size Determination

Approximately 24 patients will be enrolled during the Phase 1 portion (treated with escalated doses in a standard 3+3 cohort design) and 20 patients will be enrolled during the Phase 2 portion (treated at the MTD). In the Phase 1 portion, additional cohorts at doses >400 mg BID(800 mg/day) may be considered by the Sponsor if agreed by the Safety Review Committee after review of PK, PD, and safety data; if additional cohorts are considered the total number of patients in Phase 1 may increase beyond the approximately 24 projected patients. The maximum planned increase in dose between cohorts will be 200 mg as the total daily dose (e.g.,, the dose level above 400 mg BID will not exceed 500 mg BID). Consideration by the Safety Review Committee will also be given to suspending Phase 2 enrollment at the MTD, and instead adding the same total number of patients at a second dose level, the CAD. The expansion cohorts for the MTD and CAD, should they both be pursued, will not be concurrently open for enrollment. The two dose levels would instead be expanded sequentially. Consideration will also be given to enroll patients only at the CAD but not MTD level, based on the risk/benefit of therapy as judged by the investigator/medical monitor and sponsor.

The probability of observing at least one event with a prevalence rate of e.g. 30% is greater than 99% in the Phase 2 portion.

Probabilities for observing at least one event/one response for other scenarios are presented in the table below:

Prevalence rate / Response rate	Probability of observing at least one AE / one response
	Phase 2 portion (N=20)
5 %	64,2 %
10 %	87,8 %
15 %	96,1 %
20 %	98,8 %
30 %	> 99,9 %

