**6 TREATMENT AND RESTRICTIONS**

**6.1 Treatment**

**6.1.1 Treatment Regimen, Dosage, and Duration**

Patients will be treated at the dose cohort level to which they are assigned. All study drug will be self-administered orally. NS-018 will be self-administered 2 hours or more after the last meal and at least 1 hour before the next meal.

The dose levels planned and the numbers of patients in each dose level are presented below.

Once Daily (QD) Cohort [completed]			Twice Daily (BID) Cohort							
Cohort	NS-018 Total Daily Dose(mg)	No. of Patients Per Cohort	Cohort	NS-018 Total Daily Dose(mg)	No. of Patients Per Cohort					
Phase 1			Phase 1							
QD 1#	75	3-6								
QD 2#	125	3-6								
QD 3#	200	3-6	BID 1#	200 (100×2) £	3-6					
QD 4#	300	3-6		—	—					
	—	—	BID 2#	400 (200×2) £	3-6					
	—	—	BID 3#	600 (300×2) £	3-6					
	—	—	BID 4#§	800 (400×2) £	3-6					
Phase 2	MTD or lower Up to 20 patients									
MTD = maximum tolerated dose.										
£ BID dosing must be administered 12 hours apart										

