# If a DLT is experienced at any dose level, an intermediate cohort at a lower dose may be considered, as recommended by Safety Review Committee										
§ Additional cohorts at doses > 400 mg BID (800 mg/day) may be considered by the Sponsor if agreed by the Safety Review Committee after review of PK, PD, and safety data. The maximum planned increase in dose between cohorts will be 200 mg as the total daily dose (e.g., the dose level above 400 mg BID will not exceed 500 mg BID )										

During the study, a Safety Review Committee will review data from each cohort and may make dosing schedule changes based on the data review. The Safety Review Committee is described in detail in Section 13.9.

In the Phase 1 portion of the study, sequential cohorts of 3 to 6 patients will be treated with escalating doses until the MTD is established (see Section 6.1.1.3). The first patient in each cohort must be observed for at least 7 days of dosing with NS-018. If there is no clinically significant toxicity observed in that patient, enrollment in the cohort may continue. If a significant toxicity occurs, including any possible dose-limiting toxicity (DLT, see Section 6.1.1.2), the Safety Review Committee must meet and determine whether additional patients may be entered at that dose or an intermediate cohort at a lower dose should be considered. Each cohort can be assessed after at least 3 patients have completed 28 days of study drug dosing.

The Safety Review Committee can make dosing schedule changes (twice daily dosing rather than once daily dosing; intermediate dose levels if toxicity occurs that does not rise to the level of a DLT) based on pharmacodynamic, pharmacokinetic, and safety review. If twice daily dosing requires evaluation, dosing would start at one total daily dose level below the last once per day dose level that was declared safe. For example, when 300 mg QD was declared safe,

the starting dose for BID dosing would be 100 mg twice daily, 12 hours apart [representing a total daily dose 200 mg]).

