#### 6.1.1.3 Definition of Maximum Tolerated Dose

The MTD is defined as the dose at which  $\leq 1$  of 6 patients experience a DLT, with the next higher dose having at least 2 patients experiencing a DLT.

Rules for Determination of MTD	
Number of Patients Experiencing DLT During Study Treatment	Action
0/3	Escalate to the next higher dose level.
1/3	Up to 3 additional patients will be added before treating patients at a higher dose. If none of the additional patients experience a DLT, the dose will be escalated. If one of the additional patients has a DLT, the MTD will have been exceeded and 3 additional patients will be added at the previous dose to determine the MTD and recommended Phase 2 dose.
2/3	If 2 of the first 3 patients at a dose level experience a DLT, the MTD will have been exceeded and 3 additional patients will be added at the previous dose to determine the MTD and recommended Phase 2 dose.

DLT = dose-limiting toxicity; MTD = maximum tolerated dose.

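### Is a Phase 1 size of about 24 too low for the eight cohorts in the dose table, and does the missing Phase 2 maximum matter?

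*Combined protocol and SAP*

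**What the plan says.** Section 12.1 projects the Phase 1 size as follows: "Approximately 24 patients will be enrolled during the Phase 1 portion (treated with escalated doses in a standard 3+3 cohort design". It then says of cohorts above 400 mg BID that "if additional cohorts are considered the total number of patients in Phase 1 may increase beyond the approximately 24 projected patients". Section 3.1 and the synopsis also give about 24.

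Section 6.1.1 introduces its dose table with "The dose levels planned and the numbers of patients in each dose level are presented below". The table has four once-daily cohorts under the heading "Once Daily (QD) Cohort [completed" and four twice-daily cohorts, each of 3-6 patients. The text below it says that "sequential cohorts of 3 to 6 patients will be treated with escalating doses until the MTD is established", and a footnote adds: "If a DLT is experienced at any dose level, an intermediate cohort at a lower dose may be considered".

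Section 6.1.1.3 defines the MTD on six patients with at most one DLT, "with the next higher dose having at least 2 patients experiencing a DLT". After one DLT in three, "Up to 3 additional patients will be added before treating patients at a higher dose". When a dose is found to exceed the MTD, three more patients are added at the dose below. Section 6.1.2 enrols one extra patient in the cohort for each patient whose first-month compliance is under 80%.

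For Phase 2, Section 12.1 gives 20 patients at the MTD and the dose table gives up to 20. The Safety Review Committee may suspend enrolment at the MTD and instead add the same total number at the CAD. If both doses are pursued, they are expanded one after the other. The probability table in Section 12.1 is for N = 20.

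**The concern.** Taken with the dose table, 24 looks like a floor presented as a projection. Four completed QD cohorts hold at least 12 patients. A total of 24 therefore leaves at most 12 for four BID cohorts, with no room to expand any of them. Escalation is meant to run until an MTD is found, and declaring one requires six patients at that dose and at least two DLTs one level higher. Section 12.1 mentions extra cohorts above 400 mg BID but not intermediate cohorts or compliance replacements. A reader could conclude that the tabled cohorts will stay at about 24.

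The Phase 2 total looks open in a similar way. With a second dose level allowed, 20 could be an overall figure or a figure per dose.

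What would be at stake is the planned number of patients exposed in a first-in-human study. A site or ethics committee that relied on Section 12.1 alone might expect fewer patients than are eventually treated.

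**Working it through.** **Inputs.** Eight tabled cohorts (four QD, four BID) of 3-6 patients (6.1.1); the 3+3 rules and the MTD definition (6.1.1.3); Phase 2 N = 20 (12.1).

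**The plan's own figures**

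- Phase 1: 8 x 3 = 24, so the stated figure reproduces. It also equals 4 x 6, the four QD cohorts at full size.
- Phase 2 table: P(at least one) = 1 - (1 - p)^20. For p = 5, 10, 15, 20 and 30% this gives 64.15, 87.84, 96.12, 98.85 and 99.92%. The printed values agree.

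**Smallest Phase 1 totals, with every QD cohort at 3 (4 x 3 = 12)**

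- MTD at BID 1: 12 + 6 + 3 = 21
- MTD at BID 2: 12 + 3 + 6 + 3 = 24
- MTD at BID 3: 12 + 3 + 3 + 6 + 3 = 27
- All eight open, no expansion and no MTD: 24
- MTD at BID 4: 12 + 3 + 3 + 3 + 6 + 3 = 30. This needs a ninth cohort above 400 mg BID, which is the case Section 12.1 does name.

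So 24 lies inside the range that the plan can produce. The nominal upper end for eight cohorts is 8 x 6 = 48, before any compliance replacements or intermediate cohorts.

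**How far from 24 is typical?** The documents give no DLT rate, so a constant rate p across all doses is assumed. A cohort passes with 3 patients with probability a = (1 - p)^3, or with 6 patients with probability b = 3p(1 - p)^5. The mean size of a passing cohort is (3a + 6b)/(a + b). At p = 10%, a = 0.729 and b = 0.177, so the mean is (2.187 + 1.063)/0.906 = 3.59, and four completed QD cohorts average 14.35.

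The BID part was enumerated exactly under these further assumptions: the previous BID level is filled to 6 once a dose exceeds the MTD, nothing is added if BID 1 is exceeded, escalation stops after BID 4, and there are no intermediate cohorts or replacements. At p = 10% the BID mean is 13.5, which gives a total of about 27.9. Across assumed rates:

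| DLT rate | Mean N | P(N > 24) | P(N < 24) | 95th percentile | P(all eight open) |
|---|---|---|---|---|---|
| 2% | 25.3 | 0.36 | 0.005 | 30 | 0.99 |
| 5% | 26.7 | 0.63 | 0.03 | 33 | 0.92 |
| 10% | 27.9 | 0.74 | 0.09 | 36 | 0.74 |
| 15% | 27.8 | 0.69 | 0.17 | 36 | 0.54 |
| 20% | 27.0 | 0.61 | 0.25 | 36 | 0.36 |
| 25% | 25.8 | 0.51 | 0.33 | 36 | 0.22 |

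The mean is 1.3 to 3.9 patients above 24. P(N > 36) stays below 0.03 throughout.

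**Phase 2.** If k patients are enrolled at the MTD before suspension and 20 are then added at the CAD, the total is 20 + k. It reaches 40 only if the MTD group is filled first. If 20 is read as an overall cap, the total is 20.

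**The case for a change.** The best case for a change is that planned exposure in a first-in-human study should agree across sections. Section 12.1 names one way past 24, while the rules elsewhere contain several: routine expansion from 3 to 6, three patients added below a dose that exceeds the MTD, intermediate cohorts, and compliance replacements. With an MTD as the intended endpoint and all eight cohorts open, 24 cannot be met. Given that all eight open, P(N > 24) is 0.36 to 0.96 over the assumed DLT rates. The edit would be wording only, and the sponsor already knows the QD enrolment.

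Several parts of this stand. The minima of 24 and 27 are right under their conditions. Section 12.1 does not mention intermediate cohorts or replacements. No section gives a combined Phase 2 maximum for two dose levels.

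The rest is weaker. Section 12.1 does not say that cohorts above 400 mg BID are the only way past 24; it says that they may raise the total. Its own sentence names a 3+3 design, and the dose table prints 3-6 for every cohort, so the range of 24 to 48 can be read off directly. The highest conditional probabilities occur at DLT rates where all eight cohorts seldom open (0.36 at a 20% rate, 0.22 at 25%). A constant rate from 75 mg to 800 mg per day is itself only an illustration. A restated upper limit of 48 would not be firm either, because compliance replacements are enrolled within the same cohorts.

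**Conclusion.** No change follows. The Phase 1 figure is an approximate projection that the design can meet, and the modelled mean exceeds it by 1 to 4 patients. That result rests on the assumed constant DLT rates and on leaving out intermediate cohorts and replacements, which could only add patients. The 3+3 rules and the committee's review before each new cohort (Section 13.9) determine how many patients are treated; the projection does not limit it.

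The unstated Phase 2 total, 20 to 40 by reading, is a gap that does not reach the results. Section 12.4 plans no formal efficacy test and reports the objective response rate by dose level with exact intervals, so each dose level is described on the number actually treated there and in the Efficacy Population. The N = 20 table is correct for one dose level of 20 and would apply to each dose level that is filled to 20. Analysts would use actual enrolment in every denominator. Writing out a range and a maximum would leave enrolment, dose decisions and conclusions as they are.

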## 12.2

### Analysis Populations

#### 12.2.1

##### Safety Population

The Safety Population consists of all patients who receive at least one dose of study drug.

**12.2.2 Pharmacokinetic Population**

The PK Population includes all patients who receive at least one dose of study drug and have at least one evaluable PK profile.

**12.2.3 Pharmacodynamic Population**

The PD Population includes all patients who receive at least one dose of study drug and have baseline and at least one post-baseline PD assessment.

**12.2.4 Efficacy Population**

The Efficacy Population includes all patients who receive at least one dose of study drug and have baseline and at least one post-baseline efficacy assessment.

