5.2.4 Phase 2: Cycle 1, Day 15 ( $\pm 2$  days)

- Directed physical examination, including weight and spleen size by palpation;
- Vital signs (blood pressure, pulse, respiratory rate, and temperature);
- Laboratory tests (hematology, serum chemistries, and urinalysis, as listed in Appendix G);
- ECG – triplicate (pre-dose and approximately 2 hours post-dose; centrally read);
- Obtain blood samples for PK assessment (pre-dose and approximately 2 hours post-dose);
- Phospho-STAT3 (pre-dose and approximately 2 and 3 hours post-dose);
- Review patient study drug dosing diary for compliance;
- Assessment of AEs using the NCI CTEP CTCAE, version 4.0 (published 28 May 2009) (see Appendix H); and
- Concomitant medication notation.

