5.2.5 Phase 2: Cycle 1, Day 22 ( $\pm 2$  days)

- Hematology and serum chemistry are to be obtained at the referring/local doctor's office and faxed to the study site.

5.2.6 Phase 2: Cycle 2, 3, and 4, Day 1 ( $\pm 3$  days)

- Directed physical examination including weight and spleen size by palpation;
- Spleen size measurement by MRI (CT scan for patients not able to tolerate MRI) (Cycle 4 only). Imaging will be transmitted to a central imaging center for central reading;

- Vital signs (blood pressure, pulse, respiratory rate, and temperature);
- Laboratory tests (hematology, serum chemistries, and urinalysis, as listed in Appendix G);
- Serum or urine pregnancy test (female patients of childbearing potential only);
- ECG – triplicate (Cycle 2: pre-dose and approximately 2 hours post-dose, centrally read; Cycle 3 and 4: pre-dose, locally read);
- Obtain blood sample for PK assessment (Cycle 2 only; sampling time points are pre-dose and approximately 0.5, 1, 2, 3, 4, 6, and 8 hours post-dose);
- Bone marrow assessment (Cycle 4 only);
- Response assessment (IWG-MRT and ELN);
- JAK2 V617F allele burden if mutation present prior to start of therapy (Cycle 2 and Cycle 4, pre-dose);
- Phospho-STAT3 (Cycle 2 only: pre-dose and approximately 2 and 3 hours post-dose);
- Cytokine (pre-dose);
- MPN SAF (MPN-10) (Cycle 2 and Cycle 4, pre-dose);
- Review patient study drug dosing diary for compliance and distribute study drug;
- Assessment of AEs using the NCI CTEP CTCAE, version 4.0 (published 28 May 2009) (see Appendix H); and
- Concomitant medication notation.

5.2.7 Phase 2: Cycles 2, 3, and 4, Day 15; Cycles 5 and 6, Days 1 and 15 ( $\pm 3$  days)

- Hematology and serum chemistry are to be obtained at the referring/local doctor's office and faxed to the study site.

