5.2.11 Phase 2: End of Study Assessments

The following procedures will be performed within 30 days after the last dose of study drug or within 30 days after withdrawal from the study:

- Complete physical examination including weight and spleen size by palpation;
- Spleen size measurement by MRI (CT scan for patients not able to tolerate MRI) if not done within the past 8 weeks.
- Vital signs (blood pressure, pulse, respiratory rate, and temperature);
- ECOG Performance Status;
- Laboratory tests (hematology, serum chemistries, and urinalysis, as listed in Appendix G);
- ECG – triplicate or single reading if Cycle 13 or thereafter (locally read);
- Response assessment (IWG-MRT and ELN);
- MPN SAF (MPN-10);

- Collect any unused study drug and review patient study drug dosing diary for compliance, if applicable;
- Assessment of AEs using the NCI CTEP CTCAE, version 4.0 (published 28 May 2009) (see Appendix H); and
- Concomitant medication notation.

All efforts will be made to complete the end of study visit for early termination patients however review of laboratory tests obtained from referring/local doctor's office and a follow-up phone call to the patient may take place at a minimum for those patients refusing to return to the study site.

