#### 6.1.2 Compliance Control

Patient compliance will be monitored by assessing the tablet count from the drug packages returned at each visit. Patients will complete a study drug dosing diary daily that will document the time of day they took their study drug. Tablet counts will be compared by the site to the dosing diary to further assess compliance and aid patient education regarding compliance. Documentation on the electronic Case Report Form (eCRF) will account for patient compliance during each cohort. Patients will be instructed to return any unused study drug and packaging when attending clinic visits or if the patient is discontinued before the study is complete.

Patients who take  $<80\%$  of the expected prescribed regimen will be counseled on the importance of taking the study drug appropriately. If compliance is  $<80\%$  during the first month of therapy, the patient will be counseled, remain on study drug and will follow the study assessment schedule. The patient will be included in all final study analysis populations (See Section 12.2), however the patient will not be included in the data from each cohort that is reviewed by the Safety Review Committee to determine dosing schedule changes. In the event that a patient's compliance is  $<80\%$  during the first month of therapy, an additional patient will be enrolled in the cohort and their data will be included in the cohort review by the Safety Review Committee as well as in all final study analysis populations.

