**12.4 Efficacy Analyses**

Since the primary objective of this study is to evaluate the safety, tolerability, MTD, and clinically active dose of NS-018 in patients with PMF, post-PV MF, or post-ET MF, no formal hypothesis testing will be performed for efficacy parameters. Efficacy analysis will be based on the Efficacy Population.

The responses to treatment assessed using the IWG consensus criteria(Phase I) and the IWG MRT and ELN Response Criteria (Phase II)will be tabulated by dose level and visit. The number and percentage of patients achieving the response will be provided for each response level. The objective response rate (the percentage of patients with confirmed complete remission (CR), partial response (PR), or clinical improvement (CI) during the treatment period) and its 95% exact binomial confidence interval will be provided by dose level. Quality of life assessed using the MF SAF (Phase I) or MPN SAF (MPN-10) (Phase II) will be summarized by dose level and visit. Change in spleen size by MRI (CT scan for patients not able to tolerate MRI) for the Phase 2 portion will be summarized for the cohort.

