3. Clinical improvement (CI)	
Requires one of the following in the absence of both disease progression (as outlined below) and CR/PR assignment (CI response is validated only if it lasts for no fewer than 8 weeks)
 
(1) A minimum 2 -g/L increase in hemoglobin level or becoming transfusion independent (applicable only for patients with baseline hemoglobin level of less than 100 g/L).‡
 
(2) Either a minimum 50% reduction in palpable splenomegaly of a spleen that is at least 10 cm at baseline or a spleen that is palpable at more than 5 cm at baseline becomes not palpable.§
 
(3) A minimum 100% increase in platelet count and an absolute platelet count of at least <math>50,000 \times 10^9/L</math> (applicable only for patients with baseline platelet count below <math>50 \times 10^9/L</math>).
 
(4) A minimum 100% increase in ANC and an ANC of at least <math>0.5 \times 10^9/L</math> (applicable only for patients with baseline absolute neutrophil count below <math>1 \times 10^9/L</math>).

4. Progressive disease (PD)	Requires one of the following: 
	(1) Progressive splenomegaly that is defined by the appearance of a previously absent splenomegaly that is palpable at greater than 5 cm below the left costal margin or a minimum 100% increase in palpable distance for baseline splenomegaly of 5-10 cm or a minimum 50% increase in palpable distance for baseline splenomegaly of greater than 10 cm.
	(2) Leukemic transformation confirmed by a bone marrow blast count of at least 20%.
	(3) An increase in peripheral blood blast percentage of at least 20% that lasts for at least 8 weeks.
5. Stable disease (SD)	None of the above.
6. Relapse	Loss of CR, PR, or CI. In other words, a patient with CR or PR is considered to have undergone relapse when he or she no longer fulfills the criteria for even CI. However, changes from either CR to PR or CR/PR to CI should be documented and reported.

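### Treated patients who are never assessed leave the response-rate denominator, so the planned ORR can only equal or exceed the all-treated rate

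*Combined protocol and SAP*

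**What the plan says.** Section 12.2.4 admits a treated patient to the Efficacy Population only if he or she "have baseline and at least one post-baseline efficacy assessment". Section 12.4 states that "Efficacy analysis will be based on the Efficacy Population" and then defines the ORR as the percentage with confirmed complete remission, partial response or clinical improvement on treatment, with an exact binomial 95% interval for each dose level. No other analysis set is named for the ORR. Nothing in the protocol says that treated patients without an assessment count as non-responders.

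An all-treated set already exists. Section 12.2.1 reads: "The Safety Population consists of all patients who receive at least one dose of study drug". It is used for safety only.

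The protocol also shows how a treated patient can end up without any assessment. For early terminations, Sections 5.1.9 and 5.2.11 ask for every effort to complete the end-of-study visit, but accept a review of local laboratory results, and "a follow-up phone call to the patient may take place at a minimum for those patients refusing to return to the study site".

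**The concern.** Patients who die early or decline to come back have no documented response. Under the planned rule they are not counted as treatment failures; they simply disappear from the rate. Because none of them can be in the numerator, the omission moves the ORR in one direction only.

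This matters because efficacy is part of the Phase 2 primary objective (Section 2.1.2) and the study has no control arm, so nothing offsets a favourable denominator. Response rate also enters the definition of the clinically active dose (Section 6.1.1), where cohorts have 3 to 6 patients and one exclusion is visible. The protocol does not say which population that judgement uses. Early departures are plausible: Section 4.1 allows ECOG status up to 3 and a life expectancy from 12 weeks, and Phase 2 patients must be intolerant of, or refractory to or relapsed from, a prior JAK2 inhibitor.

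**Working it through.** **Can a never-assessed patient be a responder?** No. In Appendix I (Phase 1), "CI response is validated only if it lasts for no fewer than 8 weeks". The appendix sets no minimum duration for complete or partial remission, but both depend on post-baseline clinical, blood and marrow findings. In Appendix K (Phase 2) every response category must last at least 12 weeks.

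**Who is at risk of never being assessed?** Section 9 lists the efficacy assessments as treatment response, spleen size and bone marrow. With 28-day cycles, they first occur after baseline as follows:

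- Palpation, Phase 1: Cycle 1 Day 8 (Section 5.1.3).
- Palpation, Phase 2: Cycle 1 Day 15 (Section 5.2.4, "Directed physical examination, including weight and spleen size by palpation").
- Response assessment, Phase 2: Cycle 2 Day 1 = 28 + 1 = Day 29 (Section 5.2.6).
- MRI and marrow, Phase 2: Cycle 4 Day 1 = 3 × 28 + 1 = Day 85 (Section 5.2.6).
- End of study, both phases: palpation and response assessment within 30 days of the last dose or of withdrawal (Sections 5.1.9 and 5.2.11).

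So the excluded patients are those who leave before the first palpation and also do not return for the end-of-study visit.

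**The plan's own figures.** The table in Section 12.1 gives the chance of at least one event or response with N = 20. The formula 1 − (1 − p)^20 gives 64.15%, 87.84%, 96.12%, 98.85% and 99.92% for p = 5, 10, 15, 20 and 30%, which reproduces the printed values. The table takes 20 as the number of patients in whom a response can be seen. With 18 in the denominator, the value at p = 10% is 1 − 0.9^18 = 85.0%.

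**Direction and size.** Let T be the number treated, m the number never assessed and x the number of confirmed responders. The planned rate is x/(T − m) and the all-treated rate is x/T. Their ratio is T/(T − m), which is never below 1. For T = 20 it is 1.05 at m = 1 and 1.11 at m = 2.

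The documents give neither x nor m, so both are assumptions. Rates with Clopper-Pearson 95% intervals for T = 20:

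| Responders x | All treated (x/20) | 1 unassessed (x/19) | 2 unassessed (x/18) |
|---|---|---|---|
| 4 | 20.0% (5.7–43.7) | 21.1% (6.1–45.6) | 22.2% (6.4–47.6) |
| 6 | 30.0% (11.9–54.3) | 31.6% (12.6–56.6) | 33.3% (13.3–59.0) |
| 8 | 40.0% (19.1–63.9) | 42.1% (20.3–66.5) | 44.4% (21.5–69.2) |

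The shift runs from 0 (m = 0) to 4.4 points (x = 8, m = 2). The interval for 6/20 is 54.3 − 11.9 = 42.4 points wide. As a stress case, 4 unassessed with 6 responders would give 6/16 = 37.5% (15.2–64.6); nothing in the protocol suggests a number that high.

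In a Phase 1 cohort of 6 with 2 responders, one unassessed patient turns 2/6 = 33.3% (4.3–77.7) into 2/5 = 40.0% (5.3–85.3).

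**The case against.** The strongest reply is that the excluded group is close to empty and the effect has no consequence for a decision. Palpation comes early, the end-of-study visit repeats it with a response assessment, and a patient who is assessed once and then lost stays in the denominator. Section 12.4 plans no hypothesis test, and no response threshold or efficacy stopping rule is stated. Since the number of responders is reported as well as the percentage, a reader who knows how many were treated can divide. All of this stands and limits the size of the point. It does not change the direction, and a reader who divides would still have to recompute the interval while the headline figure remained the higher one.

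Section 12 also defers the description of the analysis to a Statistical Analysis Plan. No separate text of it was available, so a rule there cannot be excluded.

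Two stronger readings are tempting and are not supported:

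- A reader might infer that the qualifying assessment is undefined, so that a Phase 2 patient leaving on Day 20 is arbitrarily in or out. Section 12.2.4 carries no cross-reference, but Section 9 is the protocol's list of efficacy assessments, and Section 9.2 includes palpation. On that natural reading, a patient who attended the Day 15 visit is in. Day 8 hematology in Phase 2 is a safety laboratory test under Section 8.4, so it is a weak candidate for admitting anyone.
- A reader might infer a competing rule from Section 6.1.2, which says of a patient with under 80% compliance in the first month that "The patient will be included in all final study analysis populations". That sentence goes on to refer to Section 12.2, so it points to the population definitions and does not override them. Its sense is that low compliance alone does not exclude a patient, and the preceding sentence keeps such patients on the assessment schedule.

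**Conclusion.** The point holds as a small, one-directional bias. Sections 12.2.4 and 12.4 together remove never-assessed treated patients from the ORR denominator, and nothing else in the protocol puts them back. With 1 or 2 such patients among 20 and 4 to 8 responders, all assumed, the Phase 2 ORR rises by 1.1 to 4.4 points; with none, it does not change. That is small against an interval of about 42 points. In a Phase 1 cohort one exclusion can move the rate further, by 6.7 points in the 2-of-6 example.

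The point does not rest on any gap in the definition of an efficacy assessment or on a conflict with the compliance rule. It affects an estimate and its interval, not a type I error rate. It is worth correcting because the estimate serves a primary objective without a comparator and the correction is nearly free. It would lapse if the Statistical Analysis Plan already specifies an all-treated ORR.

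**What to change.** In Section 12.4, and in the Statistical Analysis Plan:

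- Make all treated patients, i.e. the existing Safety Population, the primary denominator for the ORR and its exact interval, in each phase and at each dose level.
- Count patients with no post-baseline efficacy assessment as non-responders, and report how many there were and why.
- Keep the ORR in the Efficacy Population as a sensitivity analysis.

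A cross-reference from Section 12.2.4 to Section 9 would be a helpful but optional clarification. Section 6.1.2 needs no edit. Nor should the qualifying assessment be narrowed to a formal response assessment, since that would remove patients with palpation only from the Efficacy Population.

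Cost: a few sentences and one extra table row, with no new data and no change to visits. The downside is that the reported ORR may be slightly lower.
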